**Is this a multi-site study (i.e. Each site has their own Principal Investigator)?**

No

**Does this protocol involve the use of animals?**

Yes  No

**4.0**

**Project Information**

**4.1 \* Has another IRB/HRPP reviewed this study or will another IRB/HRPP be reviewing this study?  
If Yes, answer the questions according to the IRB/HRPP Determination.**

Yes  No

IRB Name	Review Date	Determination
No records have been added		

#### 4.2 \* Is this a research study or a Compassionate Use/Emergency Use/HUD project?

Yes  No

#### 4.3 What type of research is this?

- Biomedical Research
- Clinical trial (FDA regulated)
- Behavioral Research
- Educational Research
- Psychosocial Research
- Oral History
- Other

Describe other:

Operational Testing and Evaluation

#### 4.4 Are you conducting this project in pursuit of a personal degree?

Yes  No

#### 4.6 \* Is this human subjects research? (As defined by 32 CFR 219)

**Human subject means a living individual about whom an investigator (whether professional or student) conducting research:**

- (i) Obtains information or biospecimens through intervention or interaction with the individual, and uses, studies, or analyzes the information or biospecimens; or
- (ii) Obtains, uses, studies, analyzes or generates identifiable private information or identifiable biospecimens.

Yes  No

#### 4.7 \* Do you believe this human subjects research is exempt from IRB review?

Yes  No

**Will you have a Research Monitor for this study?**

Yes  
 No  
 N/A

6.0

**Data/Specimens****6.1 Does the study involve the use of existing data or specimens only (no interaction with human subjects)?**

Yes  No

7.0

**Funding and Disclosures****7.1 Source of Funding:**

Funding Source	Funding Type	Amount
No records have been added		

Total amount of funding:

**7.2 Do you or any other Investigator(s) have a disclosure of a personal interest or financial nature significant with sponsor(s), product(s), instrument(s) and/or company(ies) involved in this study?**

Yes  No

If Yes, complete and attach Conflict of Interest forms for all key personnel

8.0

**Study Locations****8.1 Is this a collaborative or multi-site study? (e.g., are there any other institutions involved?)**

Yes  No

### 8.3 Are there international sites?

Attach international approval documents, if applicable, when prompted. Note: Ensure local research context has been considered

Yes  No

### 8.4 Is this an OCONUS (Outside Continental United States) study?

Yes  No

Select the area of responsibility:

Have you obtained permission from that area of responsibility? (This is a requirement prior to study approval)

Yes  No

## 9.0 Study Details

### 9.1 Key Words:

Provide up to 5 key words that identify the broad topic(s) of your study

Battlefield acupuncture, pain

### 9.2 Background and Significance:

Include a literature review that describes in detail the rationale for conducting the study. Include descriptions of any preliminary studies and findings that led to the development of the protocol. The background section should clearly support the choice of study variables and explain the basis for the research questions and/or study hypotheses. This section establishes the relevance of the study and explains the applicability of its findings

The use of acupuncture has increased in popularity and scope in the United States over the last several decades with some 20 million Americans estimated to have tried acupuncture at least once and between 2000 and 2010 acupuncture visits tripled. Though acupuncture is used to treat many ailments such as nausea, allergies, hot flashes, etc., its most common use is for alleviation of pain. The way that acupuncture reduces pain is explained largely by "gate theory" first cited in western literature in 1965 by [name] "The gate control theory of pain ... proposes that a mechanism in the dorsal horns of the spinal cord acts like a gate that inhibits or facilitates transmission from the body to the brain on the basis of the diameters of the active peripheral fibers, as well as the dynamic action of brain processes" The pain theory was expanded further by neuroscientist Zang-Hee Cho in 1998 via functional MRI when he showed that the visual and auditory cortices of the brain were stimulated during acupuncture. He drew further conclusions concerning the activation of beta-endorphins through the endocrine and autonomic systems which gave objective data to support gate theory. Although this and

other studies have shown promising insights into the physiological mechanisms behind acupuncture, there have been considerable doubts raised against acupuncture's place in treating pain.

In 2009, a meta-analysis synthesized data from 13 RCTs comparing acupuncture, sham-acupuncture, and no acupuncture in the treatment of pain. The authors concluded that a small analgesic effect was found when comparing acupuncture and sham acupuncture to no acupuncture, however, it was unclear if this effect was clinically significant. They state in their conclusion that, " Whether needling at acupuncture points, or at any site, reduces pain independently of the psychological impact of the treatment ritual is unclear. However, in 2018 a meta-analysis using 39 trials and over 20,000 patients compared pain and function outcomes of acupuncture, sham-acupuncture and no acupuncture. They found a 0.5 SD difference between acupuncture and no acupuncture and 0.2 SD difference with sham acupuncture which were both significant at  $P<0.001$  in the short term and even at one year 15% improvement. Another meta-analysis of 59 trials, but only 4980 patients validated its use in treating musculoskeletal pain specifically. In 2018, the academy of family physicians (AAFP) cited several other studies that further supported the effective nature of acupuncture for chronic pain making acupuncture practice for pain that more mainstream^7 and in 2019, Medicaid began coverage acupuncture for the treatment of lower back pain in conjunction with NIH trials due to the mounting evidence and a desire to combat the opioid epidemic. Other government departments have implemented acupuncture for similar reasons.

Acupuncture, among other pain management modalities, was studied at length by a task force in 2009 and 2010 with representation from Army, Navy, Air Force and the Veterans Affairs (VA). They ultimately made 109 recommendations for pain management that included the integration of acupuncture. The Department of Defense (DOD) began employing acupuncture to treat a wide array of conditions such as post-traumatic stress disorder, traumatic brain injury, polytrauma, and musculoskeletal pain at dozens of MTFs. Funding for training and education was provided from a joint incentive fund (JIF) including \$5.4 million that was shared between the DOD and the VA and ultimately led to standard teaching of battlefield acupuncture (BFA). BFA is a subcategory of auricular/ear acupuncture that gained its name because of the rapid way and in the austere environment in which it could be applied. USAF Col (Ret) Richard Niemtzow originally introduced and advocated for BFA as an efficient, cost-effective means to treating acute pain on the battlefield while still allowing active duty military members to return to duty with limited interference on capability. Several pilot studies and case studies in the military have strengthened advocacy for and expanded application of BFA in the acute treatment of MSK among many other ailments. In one focused trial at Nellis AFB, 172 patients were observed over the course of one year for treatment of chronic pain and they found a 45% reduction in opioid use and comparable reductions in muscle relaxants and NSAID use. Furthermore, they reported improved pain control and functionality.

Training providers on how to perform BFA is streamlined in the DOD. Where it used to be a course reserved for physicians, it is now taught to nurse practitioners, physical therapists, medical technicians and special forces providers and can be completed in 4 hours for Level 1 and 8 hours for Level 2 training. BFA training was originally centralized at Andrews AFB under [name] at the center of acupuncture and integrative medicine (AIM). Although it is now taught at many sites in the DOD and VA by hundreds of instructors, the approach remains the same and includes a stepwise progression of needles into five different points in the ear: Cingulate Gyrus on one ear then the other followed sequentially by the Thalamus, Omega 2, point zero and Shen Men. After each needle the patient's pain is reassessed. If analgesic effect is reached, there is no need to continue with the subsequent needles. The common needles in DOD practice are found in the chart below provided in a recent procedure instruction by the Defense Health Agency (DHA) in February 20, 2020^16:

Needle J-type No2 (.18) x 15 mm
Needle L-type No3 (.20) x 30mm
Needle L-type No5 (.25) x 40mm
Needles L-type No5 (.25) x 60mm
ASP Auricular Semi-Permanent needles, Gold
ASP Auricular Semi-Permanent needles, Stainless Steel
Pyonex Press Needles by Seirin Yellow, 0.2 x 0.6 mm
Pyonex Press Needles 0.2 x 0.9 mm

In the same report the DHA codified BFA and other forms of acupuncture and the common clinical settings in which it can be administered. Despite the wide acceptance of BFA in the DHA and the

VA and the recently published procedural instruction there is no research that compares the commonly used needles against one another in terms of patient preference and treatment outcome. The Las Vegas VA Medical Center has chosen to use pyonex needles exclusively because of improved patient compliance whereas the DOD seems to prefer the ASP needles for ease of administering, but neither practice is well substantiated by research. This pilot study will seek to answer the question of if there is any significant difference between BFA needles and if so which has best overall results when considering both symptom relief and patient tolerance of treatment.

### **9.3**

#### **Objectives/Specific Aims/Research Questions:**

Describe the purpose and objective(s) of the study, specific aims, and/or research questions/hypotheses

##### **Aim**

The aim of this pilot study is to conduct an unblinded pilot randomized clinical study on the effectiveness and tolerability of auricular semi-permanent (ASP) vs intradermal (long), and pyonex needles in Battlefield Acupuncture (BFA) for the treatment of pain.

##### **Goals**

1) Begin to identify which of 3 needles is most efficacious for BFA treatment of pain; 2) Identify patient experiences and tolerance of three commonly used acupuncture needles at Mike O'Callaghan Military Medical Center at Nellis Air Force Base. This study will compare 30 patients (10 per needling group) and will serve as a pilot study for a potential larger randomized control trial (RCT) across multiple MTFs in the Defense Health Agency (DHA) to establish better BFA care practices. We will be recruiting a total of 39 subjects, which is inclusive of a 30% drop out rate to accommodate those that may be lost to the study or have missing data to achieve a final total of 30 subjects.

##### **Hypothesis**

1) There is a difference in BFA effectiveness and tolerance between ASP, long, and pyonex needles for the treatment of acute MSK pain. 2) Pyonex needles are the most effective and tolerated acupuncture needle for the BFA treatment of pain.

### **9.4 Study Design:**

Describe study design in one to two sentences (e.g., prospective, use of existing records/data /specimens, observational, cross-sectional, interventional, randomized, placebo-controlled, cohort, etc.). Specify the phase – Phase I, II, III, or IV – for FDA-regulated investigational drug research

Randomized clinical trial comparing ASP, long, and pyonex needles by recruiting and treating 13 patients per group with the goal of analyzing at least 10 patients' questionnaires per group comparatively for effect and tolerance of different BFA needles.

### **9.5 Target Population:**

Describe the population to whom the study findings will be generalized

Active Duty members and DoD beneficiaries, 18 years or older, meeting the inclusion/exclusion criteria will be recruited.

### **9.6 Benefit to the DoD:**

State how this study will impact or be of benefit to the Department of Defense

BFA use and application is widespread. Needle phobia prevents many patients from seeking care, and prior experience with painful ASP needles prevents patients from returning for a second treatment. If we determine that other, less painful needles are as effective and better tolerated as ASP needles, then the uptake of acupuncture in the DoD will increase.

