**Sub-group Analysis:** Analysis will center on differences between the three needle groups. The three treatment groups will allow inferences to be made as to whether each group is statistically different from one another. Medication is a potential confounder, but will be addressed by standardizing the dosage of analgesics used by all subjects rather than as a variable in a general linear model with the needle group variable.

Null Hypotheses:

H01 — there is no difference in means of the DVPRS between needle groups; and

H02 — there is no difference in means of the DVPRS between repeated measures; and

H03 — there is no difference in the distribution of the tolerance ordinal scales between needle groups.

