## 11.2 Sample Size:

A priori power analysis was performed using the DVPRS variable as described below. The analysis indicates a minimum of 10 subjects in each needle group, for a total sample size of 30, will have a power of 0.44 to detect the minimal clinically important difference at alpha = 0.14. We will be recruiting a total of 39 subjects, which is inclusive of a 30% drop out rate to accommodate those that may be lost to the study or have missing data to achieve a final total of 30 subjects.

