## 11.6 Data Analysis Plan: Complete description: Background, Objectives, Design, Step by Step how the project is going to be done, Data analysis plan:

Sample and needle group means, standard deviations, medians, interquartile ranges (IQR) and ranges will be calculated for interval variables. Frequency distributions will be produced for nominal and ordinal variables.

The null hypotheses H01 and H02 for the DVPRS outcome measure will be tested by a mixed effects repeated measures analysis of variance (rANOVA). In the event a null hypothesis is rejected, contrasts will be used to investigate effects and differences between and within research and time groups. Null hypotheses H03 will be tested with Chi Squared or Fisher's Exact tests. The significance level of multiple comparison tests will be corrected to  $\alpha = .05$  by the Holm method. [6]

[name], Senior Research Biostatistician Subject Matter Expert for Clinical Research Management under contracts OMNI 0004 3-82 and OMNI 0005 3-126, is the statistical consultant supporting this study. Statistical analysis will be performed with R Version 3.5.1. [7]

[6] Holm, S. 1979. A simple sequential rejective multiple test procedure. Scand. J. Statistics, 6: 65-70.

[7] R Core Team. R: A language and environment for statistical computing. R Foundation for Statistical Computing, Vienna, Austria. 2016 URL <http://www.R-project.org/>.

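### The stated benefit depends on other needles being as effective as ASP, but the plan tests only for a difference and guarantees no needle-versus-ASP difference with an interval if that test is not significant.

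*Combined protocol and SAP*

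**What the plan says.** Section 9.6 (Benefit to the DoD) makes the expected benefit conditional: "If we determine that other, less painful needles are as effective and better tolerated as ASP needles", then uptake of acupuncture will rise.

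The hypotheses in Section 9.3 point elsewhere. The first is that "There is a difference in BFA effectiveness and tolerance between ASP, long, and pyonex needles for the treatment of acute MSK pain". The second is that "Pyonex needles are the most effective and tolerated acupuncture needle for the BFA treatment of pain".

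Section 11.1 states the effectiveness null as "there is no difference in means of the DVPRS between needle groups" (H01), alongside a null of no change over the repeated measures (H02). Section 11.6 tests both by mixed-effects repeated-measures ANOVA and adds: "In the event a null hypothesis is rejected, contrasts will be used to investigate effects and differences". It also promises group means, SDs, medians, IQRs and ranges without condition, and sets multiple comparisons to .05 by the Holm method.

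Section 11.2 says that 10 analysed subjects per group "will have a power of 0.44 to detect the minimal clinically important difference", at alpha = 0.14. No section gives an equivalence or non-inferiority hypothesis, a margin, or a confidence interval for a difference between needles. No section says how a non-significant H01 will be interpreted.

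**The concern.** The claim in Section 9.6 has two parts: pain relief no worse than with ASP, and better tolerance. A test of no difference can contradict the first part but cannot support it, because failure to reject may simply reflect few subjects. Support has to come from an estimated difference and its precision, and the plan makes the contrasts that would supply these conditional on a rejection.

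If relief really is similar, which is the case Section 9.6 describes, H01 will usually not be rejected. The reader may then have only three sets of group summaries and a p-value. What is at stake is an unsupported statement about needle choice, and a pilot that leaves out the quantities most useful for planning the larger trial.

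**Working it through.** **Inputs from the plan.** DVPRS mean 4.4, SD 2.4, and a minimal clinically important difference of 25% (Section 11.5); 10 analysed per group, 30 in all (11.2, 11.5); four DVPRS measurements (11.1); alpha 0.14 for power (11.2, 11.5); .05 for multiple comparisons (11.6).

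**Assumed.** The within-subject correlation r, which the documents do not give. A range is shown.

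**1. Effect size.** 0.25 × 4.4 = 1.1 points. d = 1.1/2.4 = 0.458. f = d/2 = 0.229.

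**2. Reproducing the stated power.** Between-groups test in a repeated-measures design, 3 groups, m = 4, N = 30, r = 0.5:

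λ = f² × N × m / (1 + (m − 1)r) = 0.229² × 30 × 4 / 2.5 = 2.52 (unrounded f), with 2 and 27 degrees of freedom.

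Power at alpha 0.14 is 0.442, which matches the stated 0.44. The match is not unique: f = 0.25 with two measurements and r = 0.5 also gives 0.44. On the plan's own figure the miss rate is 1 − 0.44 = 56%, and it belongs to alpha 0.14.

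**3. The same test at alpha 0.05.**

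| r | Power at 0.05 |
|---|---|
| 0.3 | 0.32 |
| 0.5 | 0.25 |
| 0.7 | 0.21 |

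**4. Precision of one needle-versus-ASP difference.**

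Half-width of the 95% interval = t(0.975, 27) × 2.4 × √(v × 2/10), with t = 2.052.

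- One visit, v = 1: 2.052 × 2.4 × √0.2 = 2.20 points.
- Mean of all four measurements, v = (1 + 3r)/4: 1.52 (r = 0.3), 1.74 (0.5), 1.94 (0.7).
- Mean of the three post-treatment visits adjusted for baseline, v = (1 + 2r)/3 − r². This is not the planned analysis and is shown as a favourable case: 1.42 (r = 0.5), 1.23 (0.7), 1.05 (0.8).

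**5. What this means against 1.1 points.** Here 1.1 is only a yardstick. The first result column is the chance that the 95% interval excludes a 1.1-point disadvantage when two needles are truly identical. The second is the chance that a two-sided 5% pairwise test misses a true 1.1-point difference. Both use the noncentral t with 27 degrees of freedom and shift 1.1/SE.

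| Estimator | Excludes 1.1 if identical | Misses a true 1.1 |
|---|---|---|
| One visit | 17% | 83% |
| Adjusted three-visit mean, r = 0.5 | 33% | 67% |
| Adjusted three-visit mean, r = 0.7 | 43% | 57% |
| Adjusted three-visit mean, r = 0.8 | 55% | 45% |

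**The case against.** The strongest reply is that Section 9.6 answers a form prompt about benefit. It is one conditional sentence, not an objective or a decision rule. The formal hypotheses in Section 9.3 expect a difference with Pyonex best, and difference tests fit them. The study is labelled a pilot, its goal is to begin to identify the best needle, and its low power is disclosed. All of this stands, and it makes the point one of reporting and wording rather than a flaw in the design.

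The reply also limits what may be claimed. A reader might infer any of the following, and the documents do not support them:

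- *The sponsor will treat a non-significant result as equivalence.* No section says so. The supportable statement is that the result could be misread that way, since nothing rules it out and Section 9.6 invites it.
- *A non-significant H01 leaves no information on the needle differences.* Group means and SDs are reported regardless, so differences can be worked out. The trigger is also rejection of any null, so rejecting H02 might open between-needle contrasts. What is missing is a guaranteed difference with its interval.
- *A tolerance advantage for Pyonex is the likely result, so a less effective needle would be adopted.* The plan gives no tolerance data and no power for tolerance, and a larger trial is foreseen before practice changes.
- *The plan's margin is 1.1 points.* That figure is the difference used for power. The plan sets no margin.
- *The pilot could never exclude a 1.1-point disadvantage.* Under the favourable analysis with r = 0.8 it would do so in 55% of trials with identical needles.

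Pilot status does not remove the remaining gap. A pilot's main product is estimates with their precision, and conditional contrasts may withhold exactly those.

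**Conclusion.** The point holds in a limited form. Section 9.6 rests on a finding of similar effectiveness that no planned test can supply, and if H01 is not rejected the plan does not guarantee the estimate and interval that would bear on it.

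On the plan's own figure, a real difference of 1.1 points is missed 56% of the time at alpha 0.14. At 0.05 the power is about 0.25, or 0.32 to 0.21 for correlations of 0.3 to 0.7. A pairwise 95% interval is about ±2.2 points at one visit and ±1.4 to ±1.05 under a baseline-adjusted three-visit mean with correlation 0.5 to 0.8. The pilot is therefore unlikely to establish as effective, although that is not impossible at the highest correlation considered.

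These sizes rest on the plan's SD of 2.4, 10 analysed per arm, the assumed correlations, and 1.1 points as a yardstick. The gap in reporting depends on none of the assumed values.

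**What to change.** In Section 11.6, state that the Pyonex-ASP and long-ASP differences in DVPRS will be reported with 95% confidence intervals whether or not H01 is rejected, and that non-rejection will not be taken as evidence of equal effectiveness.

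In Section 9.6, say that this pilot will estimate the differences between needles and inform the margin and size of the larger randomised trial, and that it is unlikely to establish similar effectiveness itself.

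A rule allowing the claim when an interval excludes 1.1 points is not advised. It would fix an unjustified margin in a 30-person pilot that is itself meant to inform that margin.

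The cost is a few sentences and two intervals from data already collected, with no extra subjects or visits. The downside is a more modest claim for the pilot.

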## 10.0

### Study Procedures, Data Management, and Privacy

#### 10.1 Study Procedures:

Describe step-by-step how the study will be conducted from beginning to end

Active duty members and DoD beneficiaries, age 18 years or older, meeting the inclusion/exclusion criteria will be offered an opportunity to participate. They will be recruited from the clinics located at 99MDG (Nellis AFB). All of the below items are research-related unless marked as 'standard of care':

